## 3.3 Early Withdrawal of Subjects

### 3.3.1 Criteria for removal from study

1. Procedure converted from laparoscopic to open
2. Patient who will have more than 20 % change in hemodynamics from their pre-operative values after induction of anesthesia

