### 3.3.2 Follow-up for withdrawn subjects

1. Patients who are withdrawn from the study prior to administration of anesthesia will not be followed.
2. Patients who are included in the study but removed under Section 3.3.1 will continue to be followed for 24 hours and opiate use, pain scores and vital signs recorded.

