## 7.2 Study Procedures

### 7.2.1 Day 1 –Screening and Consent

Patient will initially be identified by the surgeon. These will be patients scheduled for laparoscopic sleeve gastrectomy. Information regarding the study will be provided to the subject at this time. Consent will take place in either the surgeons office, the anesthesia clinic, or in SDU on the day of surgery. Prior to consent the patient will be screened using a screening questionnaire. Prior to the study team asking these questions, the patient will be advised that by answering these screening questions they are allowing the study team to use this information for screening purposes. If they meet the criteria to be included into the study, a member of the research team will obtain written consent from the patient. Patients will be advised that although they are being consented for the study, the ultimate decision on whether they will be included will be made based on their time of surgery (OR schedule). If a patient is scheduled for surgery less than 24 hours following the previous patient, they will be withdrawn from the study.

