## 9.0 Statistical Plan

### 9.1 Sample size determination

Up to 250 subjects will be enrolled in order to obtain enough data to determine if a significant difference exists between the treatment groups. This number will allow exclusions and withdrawals, in order to obtain the goal of 36 completed subjects per group.

Based on the Martinez study, the mean (and standard deviation) for the 48-hour morphine use in the ketamine group was 52 mg + 22 mg. Assuming that magnesium would yield a similar result as ketamine, a conservative expectation for the combination of ketamine and magnesium is a 25% reduction for the 24-hour morphine use to 19.5 mg. In order to achieve 80% statistical power with one-sided, 0.05 statistical tests, a sample size of 36 for each of the three groups is needed (total sample size of 108 completed patients for statistical analysis).

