### 9.2 Statistical methods

Our current plan is to use ANOVA, along with pairwise comparisons, to compare the three groups with respect to pain scores (nonparametric ANOVA) and total hydromorphone use (parametric ANOVA) in the first 24 hours post-operatively, to determine whether there are any significant differences. We will use SAS, Version 9.4, for all statistical analyses.

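### Randomised patients can be removed for a haemodynamic change that the study drug may cause, and the plan does not say whether they are analysed

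*Combined protocol and SAP*

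**What the plan says.** Section 3.3.1, item 2, lists as grounds for removal: "Patient who will have more than 20 % change in hemodynamics from their pre-operative values after induction of anesthesia". The haemodynamic variable, the direction and duration of the change, and the end of the window are not given.

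The order of events is as follows. Randomisation falls on the day before surgery (Section 7.2.2) or on the day of surgery (Section 7.4.3). These two statements need reconciling, but under either the allocated drug is prepared before it is given. Sections 7.2.4 and 7.4.6.3 put the 10-minute infusion after the endotracheal tube is secured, so after induction. Patient and anaesthesia team are blinded (Section 7.2.2).

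Section 12.0 lists hypertension, hypotension, tachycardia and bradycardia for ketamine, and hypotension and depressed cardiac function for magnesium. It calls these uncommon and says most were noted at higher doses.

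On follow-up, Section 3.3.2 says of patients removed under 3.3.1 that they "will continue to be followed for 24 hours and opiate use, pain scores and vital signs recorded". By contrast, "Patients who are withdrawn from the study prior to administration of anesthesia will not be followed".

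On numbers, Section 9.1 allows up to 250 enrolled: "This number will allow exclusions and withdrawals, in order to obtain the goal of 36 completed subjects per group", a "total sample size of 108 completed patients for statistical analysis". Section 9.2 plans ANOVA with pairwise tests "to compare the three groups with respect to pain scores (nonparametric ANOVA) and total hydromorphone use (parametric ANOVA"). It names no analysis population and does not say how removed patients are handled.

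**The concern.** A comparison of randomised groups is protected only while membership of the analysed groups does not depend on what happened after treatment began. Here a removal rule runs during and after the infusion, and its trigger is something the protocol lists as a possible effect of the drugs. Against saline, either drug could trigger removal. In the contrast that Section 9.1 sizes, combination versus ketamine alone, both arms receive ketamine, so a difference could come only from adding magnesium.

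If removed patients are dropped and recruitment continues until 36 per group complete, the numbers are restored but comparability is not. The primary endpoint, 24-hour hydromorphone use, would be compared between groups filtered by their response to treatment. Because *completed* is undefined, two analysts could follow this plan faithfully and analyse different patients.

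**Working it through.** **1. When selection bias arises.** In an arm, let p be the fraction removed, K the mean opioid use of those kept and R that of those removed. The mean of all patients is M = (1 − p)K + pR, so K − M = p(K − R). With no treatment effect, M is the same in the active arm (A) and the control arm (C). The expected difference among those kept is then

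K_A − K_C = p_A(K_A − R_A) − p_C(K_C − R_C).

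- If removal is triggered only between induction and the start of the infusion, no study drug has been given and the team is blinded. In expectation p and (K − R) are then equal across arms, and the difference is zero.
- If removal can be triggered during or after the infusion, p, (K − R) or both may differ by arm. Equal removal counts do not guarantee zero: the criterion has no direction, so one arm could lose patients for a rise and another for a fall.
- If removed patients do not differ in opioid use from those kept, the difference is zero.

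The documents give none of p_A, p_C, (K_A − R_A) or (K_C − R_C). Size and sign are therefore unknown.

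**2. The plan's sample size.** Inputs from Section 9.1: 48-hour morphine use of 52 mg, SD 22 mg, in the ketamine group; "a conservative expectation for the combination of ketamine and magnesium is a 25% reduction for the 24-hour morphine use to 19.5 mg"; one-sided 0.05; 80% power. Halving to 24 hours (inferred) gives 26 mg and SD 11 mg, so the target is 26 − 19.5 = 6.5 mg.

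n = 2 × (1.645 + 0.842)² × (11/6.5)² = 35.4, i.e. 36 per group. This reproduces the stated figure. A two-sided test would give 45, and an SD left at 22 mg would give 142, so one-sided with SD 11 is evidently what was used. The noncentral t test gives 79.9% power at 36 per group.

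**3. Cost of keeping removed patients in.** This applies to combination versus ketamine only, because no active-versus-saline target is stated. Take the extreme case of no effect at all in removed patients. A removal fraction p (assumed: 10% and 20%) shrinks the effect to 6.5(1 − p). Power comes from the one-sided t test with noncentrality effect / (11 × √(2/n)).

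| Removed | Effect (mg) | n per group | Noncentrality | Power |
|---|---|---|---|---|
| 0% | 6.50 | 36 | 2.51 | 80% |
| 10% | 5.85 | 36/0.9 = 40 | 2.38 | 76% |
| 20% | 5.20 | 36/0.8 = 45 | 2.24 | 72% |
| 10% | 5.85 | 36 in total | 2.26 | 72% |
| 20% | 5.20 | 36 in total | 2.01 | 63% |

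The n = 40 and n = 45 rows add removed patients to 36 completers per group; the last two rows count them inside the 36. The SD is held at 11. Mixing responders with non-responders raises the combination-arm variance from 121 to 121 + 6.5² × p(1 − p) = 124.8 or 127.8, which costs about one further point at most. To hold 80% in this extreme case, 35.4/0.9² = 43.7 (44 per group) or 35.4/0.8² = 55.3 (56 per group) would be needed.

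**The case against.** The strongest reply is that nothing in the plan excludes these patients. The only operational instruction about them keeps them under 24-hour follow-up and records opiate use, which yields the primary endpoint, and *completed* could mean having 24 hours of data. This stands in part. A reader might infer that the plan states a completer analysis; it does not. Removal from the study and a count of completed patients point that way, but exclusion is suggested, not stated.

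A reader might also take 250 − 108 = 142 as the expected number of such removals. That does not follow. The allowance covers every kind of loss, including scheduling ("If a patient is scheduled for surgery less than 24 hours following the previous patient, they will be withdrawn from the study") and withdrawals before anaesthesia, and no removal rate is given.

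Blinding prevents removal based on knowing the arm, but not removal set off by the drug's own effect. That the listed effects are uncommon makes a large imbalance less likely, and this stands. However, Section 12.0 lists adverse effects; it gives no frequency of changes above 20% from pre-operative values.

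The sponsor may have meant only the response to induction agents. On that reading the risk is nil. The text does not say so. Sections 3.3.1 and 7.2.4 do not contradict each other; the window simply has no stated end.

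Finally, conversion to open surgery (Section 3.3.1, item 1) is a different matter. No dependence on arm is argued for it here, and the stated question concerns laparoscopic surgery.

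**Conclusion.** The point holds as a risk that the plan leaves open, and it should be fixed. As written, randomised patients can be removed for an event that the study drug may cause, and the plan does not say whether they count in the primary analysis. Bias needs three things together: removed patients are left out, removal differs by arm in rate or direction, and haemodynamic change is related to opioid use. The documents establish none of the three.

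A reader might infer that the trial is biased, or put a figure in mg on it. Neither is supported: any such figure would rest on removal rates and a correlation that the documents do not contain. The stated sample size is not in dispute. Confidence is medium, because everything turns on the intended window and the meaning of *completed*.

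**What to change.** - In Section 9.2, state that the primary analysis includes every randomised patient in whom anaesthesia was induced, in the assigned group, including those removed under 3.3.1, using the 24-hour opiate data of Section 3.3.2. Defining the set by induction rather than by receipt of study drug also keeps patients removed between induction and infusion. Those withdrawn before anaesthesia, who are not followed, left before any study drug was given.
- Define *completed* and report completers as a sensitivity analysis.
- Keep conversions to open surgery in the primary set as randomised, with a sensitivity analysis without them.
- Tabulate removals by arm, reason, direction of change and timing relative to the infusion.
- Ask the sponsor to clarify the window in Section 3.3.1 relative to the infusion in Section 7.2.4. No change to the clinical threshold is proposed.

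The cost is wording in Sections 3.3 and 9; no extra data are needed for patients removed under 3.3.1. The downside is some dilution and added variance, at worst as tabulated above. Counting removals in addition to 36 completers per group limits the loss and fits Section 9.1's existing goal: 3 × 45 = 135 analysed at 20% removal, against a ceiling of 250 that must also absorb other losses.

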### 3.3.2 Follow-up for withdrawn subjects

1. Patients who are withdrawn from the study prior to administration of anesthesia will not be followed.
2. Patients who are included in the study but removed under Section 3.3.1 will continue to be followed for 24 hours and opiate use, pain scores and vital signs recorded.

# 4.0 Recruitment Methods

## 4.1 Identification of subjects

Patients will be initially identified by the bariatric surgical team in their clinic and the scheduler will notify anesthesia of potential study patients.

## 4.2 Recruitment process

The primary surgical team will advise the patients that they are eligible for the study and they will receive more information from the anesthesia team about this at either their anesthesia pre-op visit or on the day of surgery. The surgeon will give the patient a handout describing the

study. Patients will be officially recruited to the study when they are seen in the anesthesia clinic or in the Same Day Unit (SDU) prior to their operation. At this time the patient will be screened using a screening questionnaire. Prior to the study team asking these questions, the patient will be advised that by answering these screening questions they are allowing the study team to use this information for screening purposes. If the patient meets the criteria to be included into the study, a member of the research team will obtain consent from the patient.

#### **4.3 Recruitment materials**

Screening questions: see the attached document  
Study handout

#### **4.4 Eligibility/screening of subjects**

All potential subjects will be asked screening questions (see screening document). If eligible, subjects will be offered enrollment in the research (see section 4.2).

### **5.0 Consent Process and Documentation**

#### **5.1 Consent Process**

##### **5.1.1 Obtaining Informed Consent**

###### **5.1.1.1 Timing and Location of Consent**

Following screening (Section 4.1) written consent will be obtained. This will take place in either the surgeon's office, the anesthesia clinic or SDU.

###### **5.1.1.2 Coercion or Undue Influence during Consent**

It will be explained to the patient that research is voluntary. The patient will be encouraged to ask questions and it will be explained to the patient that their decision to participate or not participate will have no effect on their level of care.

##### **5.1.2 Waiver or alteration of the informed consent requirement**

Not applicable

#### **5.2 Consent Documentation**

##### **5.2.1 Written Documentation of Consent**

Written consent will be obtained. A signed and dated copy will be retained by the patient. A signed and dated copy will also be stored in the locked office of the research team and stored in the patient's medical record.

##### **5.2.2 Waiver of Documentation of Consent**

Implied consent will be obtained for the screening questions used to determine eligibility prior to review of the consent document and enrollment in the research study.

#### **5.3 Consent – Other Considerations**

Not applicable

### **6.0 HIPAA Research Authorization and/or Waiver or Alteration of Authorization**

#### **6.1 Authorization and/or Waiver or Alteration of Authorization for the Uses and Disclosures of PHI**

**Check all that apply:**

- Authorization will be obtained and documented as part of the consent process.
- Partial waiver is requested for recruitment purposes only (*Check this box if patients' medical records will be accessed to determine eligibility before consent/authorization has been obtained*)
- Full waiver is requested for entire research study (e.g., *medical record review studies*)
- Alteration is requested to waive requirement for written documentation of authorization

## 6.2 Waiver or Alteration of Authorization for the Uses and **Disclosures** of PHI

Waiver of Authorization is requested for the screening questions used to determine eligibility prior to review of the consent document and enrollment in the research study.

## 6.3 Waiver or alteration of authorization statements of agreement

Protected health information obtained as part of this research will not be reused or disclosed to any other person or entity, except as required by law, for authorized oversight of the research study, or for other permitted uses and disclosures according to federal regulations.

The research team will collect only information essential to the study and in accordance with the 'Minimum Necessary' standard (information reasonably necessary to accomplish the objectives of the research) per federal regulations.

Access to the information will be limited, to the greatest extent possible, within the research team.

All disclosures or releases of identifiable information granted under this waiver will be accounted for and documented.

# 7.0 Study Design and Procedures

## 7.1 Study Design

The will be a prospective, randomized, controlled, and blinded study.

## 7.2 Study Procedures

### 7.2.1 Day 1 –Screening and Consent

Patient will initially be identified by the surgeon. These will be patients scheduled for laparoscopic sleeve gastrectomy. Information regarding the study will be provided to the subject at this time. Consent will take place in either the surgeons office, the anesthesia clinic, or in SDU on the day of surgery. Prior to consent the patient will be screened using a screening questionnaire. Prior to the study team asking these questions, the patient will be advised that by answering these screening questions they are allowing the study team to use this information for screening purposes. If they meet the criteria to be included into the study, a member of the research team will obtain written consent from the patient. Patients will be advised that although they are being consented for the study, the ultimate decision on whether they will be included will be made based on their time of surgery (OR schedule). If a patient is scheduled for surgery less than 24 hours following the previous patient, they will be withdrawn from the study.

### 7.2.2 Day before surgery

A member of the research team may call the patient to ensure that they are planning on coming in for their scheduled surgery ( ie: not sick, running a fever, has transportation),, the study team will advise the investigational pharmacy that the drug for the study patient can be prepared.

The subject will then be randomized by a computer-generated randomization list using SAS software (SAS Institute, Cary, NC) and stratified in blocks of nine to allow an equal number of participants in each of three groups:

- Group 1. Ketamine group (Ketamine 0.5mg/kg + placebo for Magnesium, Normal Saline)
- Group 2. Ketamine (0.5mg/kg) plus magnesium (2g) group
- Group 3. Control group (Placebo for Ketamine, Normal Saline + Placebo for Magnesium, Normal Saline)

The patient and anesthesia team will be blinded to the group that the subject was randomized to. In the event that the patient has a concerning reaction or becomes unstable in any fashion the patient will be immediately unblinded from the study.

#### **7.2.3 Day of Surgery - Pre-op**

The patient will receive a study bracelet with his study ID number and initials to allow for study verification when the study drug is received in the operating room.

The placement of scopolamine patches are dictated on a case to case basis and are not used as a standard of care. The patch has been omitted from the protocol so that the effects of the experimental medications on PONV will not be confounded by other agents acting on PONV.

#### **7.2.4 Day of Surgery Pre-Operation and Operating Room**

During routine check of preoperative vital signs in the SDU the patient will be fitted with the Sentec CO2 monitor. Standard preoperative checklists/questions will be asked by the nursing staff as per hospital protocol.

The investigational pharmacy will deliver the appropriate study medication to the OR window, or the drug will be picked up by the coordinator at the investigational pharmacy. Prior to induction of anesthesia the patient will receive 1-2 mg of IV midazolam for anxiolysis if needed. Anesthesia will be induced with propofol (1.5-2.5 mg/kg) and fentanyl 1-2 $\mu$ g/kg. Muscle relaxant will be administered to facilitate tracheal intubation and to maintain muscular relaxation. Following securement of the endotracheal tube, the study medication will be administered over 10 minutes via an IV infusion pump. Dexamethasone 4 mg and 1 gm of Tylenol IV will be given after the study medication has been delivered, as per standard of care. Maintenance of anesthesia will be with desflurane and fentanyl dosing at the discretion of the primary team. End tidal CO2 will be maintained between 30-35 mm hg (Apollo SW4.5n, Anesthetic Gas Module, Telford,PA, USA). No long-acting opiate will be used. 4 mg ondansetron will be given during skin closure at the end of surgery. Subjects will then be fully reversed and allowed to emerge from anesthesia and will be extubated per the primary anesthesia team. The above protocol is standard care for a patient undergoing a sleeve gastrectomy. The only non-standard part of this anesthetic is the addition of the study medications.

#### **7.2.5 Post- op**

As per standard of care, the patient will be taken to the post anesthesia care unit (PACU) and set up with standard ASA monitoring as well as the Sentec CO2 monitor which was applied in the SDU.. A hydromorphone patient controlled analgesia (PCA) pump will be set-up by nursing and given to the patient. Standard dosing of 0.2 mg bolus, every 6 minutes with a maximum 2 mg per hour will be the starting dose as is standard for these patients post-operatively. As per standard of care, 1 gm of Tylenol every 8hrs will also be scheduled to be administered via IV route for 1st 24hrs. If reported pain scores are beyond the patients previously determined acceptable pain score (asked pre-operatively per hospital standard) the PACU resident may give additional doses of IV hydromorphone at his/her discretion. When patient meets discharge criteria they will be sent from the PACU to their room with monitoring of continuous pulse oximetry and ETCO2 until 24 hours post-operation.

During the post-operative period, data will be recorded immediately upon arrival to PACU and every 4 hours thereafter with a maximum recording of 24 hours post-op. For study purposes, a data sheet will be assigned to the patient pre-operatively with pre-operative pain anxiety, and PONV scores recorded. The sheet will then be attached to the patients chart and data recorded by the nursing staff. At the end of the 24 hour period the sheets will be collected by one of the research team members.

### 7.3 Duration of Participation

The patient will remain in the study for up to 24 hours postoperatively.

### 7.4 Test Article(s) (Study Drug(s) and/or Study Device(s))

#### 7.4.1 Description

#### 7.4.2 Treatment Regimen

Arms	Assigned Interventions (Each participant will receive 2 IV infusions that are labeled in a blinded manner)
Ketamine 0.5mg/kg IV dose	1. Ketamine 0.5mg/kg IV dose 2. Placebo for Magnesium Sulfate (NaCl 0.9%) IV infusion
Ketamine 0.5mg/kg IV dose Magnesium Sulfate 2 grams IV	1. Ketamine 0.5mg/kg IV dose 2. Magnesium Sulfate 2 grams IV infusion
Placebo (NaCl 0.9%)	1. Placebo for Ketamine (NaCl 0.9%) IV dose 2. Placebo for Magnesium Sulfate (NaCl 0.9%) IV infusion

#### 7.4.3 Method for Assigning Subject to Treatment Groups

Public Health Sciences will supply the randomization list to the investigational pharmacy as the research team is blinded. On the day of surgery, subjects consented for the study will be randomized by a computer-generated randomization list using SAS software (SAS Institute, Cary, NC) and stratified in blocks of nine to allow an equal number of participants in each of the three study groups.

